4.6.5.5. Immunogenicity**4.6.5.5.1. Definitions of Sample ADA Status**

At a high level, an individual sample is potentially examined multiple times, in a hierarchical procedure, to produce a sample ADA assay result and potentially multiple cross-reactive antibodies assay results and multiple NAb assay results. The cut points used, the drug tolerance of each assay, and the possible values of titers are operating characteristics of the assay.

Figure GPHL.4.1 details a flow chart that reflects the multi-tiered testing approach.

Abbreviations: ADA = anti-drug antibodies; CP = cut point; GIPR = glucose-dependent insulinotropic polypeptide receptor; GLP-1R = glucagon-like peptide-1 receptor; LY = LY3298176 (tirzepatide); NAb = neutralizing antibodies; nGIP = native glucose-dependent insulinotropic polypeptide; nGLP-1 = native glucagon-like peptide-1.

Figure GPHL.4.1. Flowchart of immunogenicity multitiered testing approach.

Table GPHL.4.7 outlines results as reported from Tier 2a of the multi-tiered testing approach. Tier 4 results are reported similarly.

Table GPHL.4.7. Sample Anti-Drug Antibodies (ADA) Assay Results

Sample Laboratory Result	Explanation
Detected	ADA are detected and confirmed.
Not Detected	The raw result as reported from the laboratory indicates not detected. The clinical interpretation of such results depends on other factors (see Table GPHL.4.8).
NO TEST, QNS, etc.	Sample exists but was unevaluable by the assay.

Abbreviations: ADA = anti-drug antibodies; QNS = quantity not sufficient.

It can be the case that the presence of high concentrations of tirzepatide will affect immunoassays, and conversely high levels of antibodies may affect the measurement of tirzepatide concentration. Thus, a tirzepatide drug concentration, assessed from a sample drawn at the same time as the ADA sample, plays a key role in clinical interpretation of a sample when the laboratory result is Not Detected (see [Table GPHL.4.8](#)).

Table GPHL.4.8. Sample Clinical ADA Interpretation Results

Sample Clinical Interpretation	Explanation
ADA Present	ADA assay result is Detected
ADA Not Present	ADA assay result is Not Detected and simultaneous drug concentration is at a level that has been demonstrated to not interfere in the ADA detection method (ie, drug concentration is below the assay's drug tolerance level). For participants receiving placebo, drug concentration is not assessed and is assumed to be below the assay's drug tolerance level. If drug concentration was planned but is not available for a treatment-period sample, a Not Detected sample will be declared ADA Not present.
ADA Inconclusive	ADA assay result is Not Detected but drug concentration in the sample is \geq the assay's drug tolerance level, which may cause interference in the ADA detection method.

Abbreviations: ADA = anti-drug antibodies.

All ADA present samples will be evaluated for cross-reactivity to native GIP (Tier 2b), cross-reactivity to native GLP-1 (Tier 2c), NAb LY (tirzepatide) on GIPR (Tier 4a), and NAb LY (tirzepatide) on GLP-1R (Tier 4b). If cross-reactivity ADA against native GIP is detected, the *in silico* assessment for cross-reactivity NAb against native GIP is evaluated, and if cross-reactivity ADA against GLP-1 is detected, the *in silico* assessment for cross-reactivity NAb against native GLP-1 is evaluated ([Figure GPHL.4.1](#)).

Similar terminology to [Table GPHL.4.8](#) applies for each type of cross-reactive and NAb assay. Importantly, each of these is a distinct assay and, in general, has different assay operating characteristics.

The following are considered inconclusive for the NAb result:

- NAb LY on GIPR: if NAb result is not detected, and PK concentration is \geq drug tolerance limit of the NAb LY on GIPR assay
- NAb LY on GLP-1R: if NAb result is not detected, and PK concentration is \geq drug tolerance limit of the NAb LY on GLP-1R assay

An *in silico* method utilizing results from Tiers 2b and 2c, Tiers 4a and 4b, and tirzepatide concentrations is used to determine cross-reactive NAb against native GIP and GLP-1. The *in silico* method is outlined in the following table (Table GPHL.4.9).

Table GPHL.4.9. In Silico Classification for Cross-Reactive NAb

In Silico Classification	Cross-reactive Binding ADA Result	NAb Result	Circulating Tirzepatide Level (ng/mL)	In Silico Cross-reactive NAb Interpretation
Cross-reactive NAb to nGIP	Tier 2b: "Not Detected"	Tier 4a: "Not Detected" or Tier 4a: "Detected" or N/A or Missing	Any Value or Missing	Not Present
	Tier 2b: "Detected"	Tier 4a: "Not Detected"	<drug tolerance limit of Tier 4a assay	Not Present
	Tier 2b: "Detected"	Tier 4a: "Not Detected"	\geq drug tolerance limit of Tier 4a assay	Inconclusive
	Tier 2b: "Detected"	Tier 4a: "Detected"	<drug tolerance limit of Tier 4a assay	Present
	Tier 2b: "Detected"	Tier 4a: "Detected"	\geq drug tolerance limit of Tier 4a assay	Present
Cross-reactive NAb to nGLP-1	Tier 2c: "Not Detected"	Tier 4b: "Not Detected" or Tier 4b: "Detected" or NA or Missing	Any Value or Missing	Not Present
	Tier 2c: "Detected"	Tier 4b: "Not Detected"	<drug tolerance limit of Tier 4b assay	Not Present
	Tier 2c: "Detected"	Tier 4b: "Not Detected"	\geq drug tolerance limit of Tier 4b assay	Inconclusive
	Tier 2c: "Detected"	Tier 4b: "Detected"	<drug tolerance limit of Tier 4b assay	Present
	Tier 2c: "Detected"	Tier 4b: "Detected"	\geq drug tolerance limit of Tier 4b assay	Present

Abbreviations: ADA = antidrug antibodies; GIP = glucose-dependent insulinotropic polypeptide; GLP-1 = glucagon-like peptide-1; NAb = neutralizing antibodies; nGIP = native glucose-dependent insulinotropic polypeptide; nGLP-1 = native glucagon-like peptide-1; Tier 2b = cross-reactive ADA to nGIP; Tier 2c = cross-reactive ADA to nGLP-1; Tier 4a = NAb LY (tirzepatide) on GIP receptor; Tier 4b = NAb LY (tirzepatide) on GLP-1 receptor.

Note that in the case of an ADA Inconclusive sample, each of the NAb and Cross-Reactive NAb assay results is taken to be Inconclusive.

Note also that any reference to an assay cut point and/or drug tolerance is population specific and is subject to modification to study-specific parameters per regulatory guidance.

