4.6.5.5.3. Definitions of Participant ADA Status

Treatment-emergent (TE) ADA-evaluable participants: a participant with a nonmissing baseline ADA result and at least 1 nonmissing postbaseline ADA result.

Treatment-emergent ADA unevaluable participant: any participant who does not meet the evaluable criteria.

Baseline ADA Present (preexisting antibody): ADA detected in a sample collected up to the first dose date and time.

Baseline ADA Not Present: ADA is not detected, and the corresponding tirzepatide PK concentration is missing or below the drug tolerance limit in a sample collected up to the first dose date and time.

TE ADA positive (TE ADA+) participant: A participant who is evaluable for TE ADA is TE ADA+ if either of the following holds:

- The participant has baseline status of ADA Not Present and at least 1 postbaseline status of ADA Present with titer $\geq 2 \times$ MRD of the ADA assay.
- The participant has baseline and postbaseline status of ADA Present, with the postbaseline titer being 2 dilutions (4-fold) greater than the baseline titer. That is, the

participant has baseline (B) status of ADA Present, with titer 1:B, and at least 1 postbaseline (P) status of ADA Present, with titer 1:P, with P/B \geq 4.

As shown in [Figure GPHL.4.1](#), a titer is expected when ADA assay result is detected. On occasion, the corresponding assay cannot be performed, in which case a titer value will be imputed for the purpose of TE ADA determination. A baseline sample with detected ADA and no titer is imputed to be the MRD (1:10) and a postbaseline sample with ADA detected and no titer is imputed to be one dilution above the MRD (1:20).

TE ADA-Inconclusive participant: a TE ADA-evaluable participant is TE ADA Inconclusive if \geq 20% of the participant's postbaseline samples are ADA Inconclusive and all remaining postbaseline samples are ADA Not Present.

TE ADA-negative (TE ADA-) participant: a TE ADA-evaluable participant is TE ADA- when the participant is not TE ADA+ and not TE ADA Inconclusive.

For each NAb assay, the following is defined:

NAb-positive (NAb+) participant: a participant who is TE ADA+ and has a Nab+ sample in the postbaseline period.

NAb-Inconclusive participant: a participant who is TE ADA+, is not NAb+, and all samples that have TE ADA+ titer have a NAb-Inconclusive sample result.

NAb-negative (NAb-) participant: a participant is neither NAb+ or NAb inconclusive.

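### Two SAP immunogenicity rules give a negative label where the SAP's own logic points to Inconclusive: the TE ADA Inconclusive definition, and Table GPHL.4.9 at or above the Tier 2b/2c drug tolerance

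*SAP*

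**What the plan says.** **Participant status (SAP 4.6.5.5.3).** An evaluable participant is TE ADA+ in either of two ways. With no antibody at baseline, at least one postbaseline titre must reach twice the minimum required dilution. With antibody at baseline, the titre must rise at least 4-fold. A participant is TE ADA Inconclusive when at least 20% of the participant's "postbaseline samples are ADA Inconclusive and all remaining postbaseline samples are ADA Not Present". Every other evaluable participant who is not TE ADA+ is TE ADA-negative.

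**Sample status (SAP 4.6.5.5.1).** The text says that a simultaneous tirzepatide concentration "plays a key role in clinical interpretation of a sample when the laboratory result is Not Detected". Table GPHL.4.8 assigns ADA Inconclusive when the "ADA assay result is Not Detected but drug concentration in the sample is" at or above the assay's tolerance. ADA Not Present requires that the "simultaneous drug concentration is at a level that has been demonstrated to not interfere in the ADA detection method". There is a stated convention for gaps: "If drug concentration was planned but is not available for a treatment-period sample, a Not Detected sample will be declared ADA Not present". Placebo samples are assumed to be below tolerance. The SAP then says that similar terminology "applies for each type of cross-reactive and NAb assay", and adds: "Importantly, each of these is a distinct assay and, in general, has different assay operating characteristics".

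**Cross-reactive neutralising antibody (Table GPHL.4.9).** If Tier 2b (native GIP) or Tier 2c (native GLP-1) is Not Detected, the output is Not Present whatever the Tier 4 result, with the tirzepatide column reading "Any Value or Missing". If Tier 2b or 2c is Detected and Tier 4a or 4b is Not Detected, the same table does use the Tier 4 tolerance limit: below it the output is Not Present, at or above it Inconclusive.

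**The concern.** Both rules err towards the reassuring category.

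The participant rule is not monotone. Replacing a clean sample by one that shows some antibody, with everything else equal, moves the participant from Inconclusive to negative. Such participants then sit in the TE ADA-negative group of the summary of hypersensitivity and injection site events by TE ADA status (SAP 4.6.5.5.4), although most of their samples may be uninterpretable.

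The table rule reports absence of antibody that could neutralise the participant's own GIP or GLP-1 from a binding test that, by the SAP's general rule, could not show absence at that drug level. It can carry forward. A TE ADA+ participant who is not NAb-positive is NAb-Inconclusive only if all samples with a TE ADA+ titre are Inconclusive, and the SAP applies this definition to cross-reactive neutralising antibody as well. One sample labelled Not Present is enough to make such a participant negative.

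**Working it through.** The documents give no rate, tolerance limit or expected count for this point, so there is no stated figure to reproduce. The check is of the rules themselves.

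**Step 1: participant rule.** Inputs:
- Minimum required dilution 1:10 (SAP 4.6.5.5.3; Protocol 9.4.6), so the threshold without baseline antibody is 2 × 10 = 20, a titre of 1:20.
- With baseline antibody, the postbaseline to baseline titre ratio must be at least 4.
- Inconclusive share of at least 20%.
- Five on-treatment samples, read from the Schedule of Activities as Weeks 4, 12, 24, 48 and 72, and six with Visit 801. The late columns are shifted in the text available, so this is a reading; the logic does not depend on it.

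| Baseline | Postbaseline samples | Inconclusive share | Meets TE ADA+? | Rest all Not Present? | Status |
|---|---|---|---|---|---|
| Not Present | 4 Inconclusive, 1 Not Present | 4/5 = 80% | No | Yes | Inconclusive |
| Not Present | 4 Inconclusive, 1 Present at 1:10 | 4/5 = 80% | No (10 < 20) | No | Negative |
| Present, 1:20 | 4 Inconclusive, 1 Present at 1:20 | 4/5 = 80% | No (20/20 = 1 < 4) | No | Negative |
| Not Present | 1 Inconclusive, 4 Not Present | 1/5 = 20% | No | Yes | Inconclusive |
| Not Present | 1 Inconclusive, 1 Present at 1:10, 3 Not Present | 1/5 = 20% | No (10 < 20) | No | Negative |
| Not Present | Six samples: 4 Inconclusive, 2 Not Present | 4/6 = 66.7% | No | Yes | Inconclusive |
| Not Present | Six samples: 4 Inconclusive, 1 Present at 1:10, 1 Not Present | 4/6 = 66.7% | No (10 < 20) | No | Negative |

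The reversal appears at 20%, 66.7% and 80% Inconclusive. A clean washout sample does not remove it.

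**Step 2: table rule.** For one receptor, take Tier 2 Not Detected with three Tier 4 states (Not Detected, Detected, N/A or missing) and three drug levels (below the Tier 2 limit, at or above it, missing): 3 × 3 = 9 combinations.

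| Drug level against Tier 2 limit | Tier 4 | Table GPHL.4.9 | Table GPHL.4.8 rule applied to Tier 2 |
|---|---|---|---|
| Below | any of 3 | Not Present | Not Present: agree |
| Missing | any of 3 | Not Present | Not Present by convention: agree |
| At or above | Not Detected | Not Present | Inconclusive: conflict |
| At or above | Detected | Not Present | Inconclusive: conflict |
| At or above | N/A or missing | Not Present | Inconclusive: conflict |

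Three of nine conflict per receptor, so 3 × 2 = 6 across GIP and GLP-1. These are cells of a rule, not participants.

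**Step 3: which of the three should change.** Where Tier 4 is Not Detected and the drug level is below the Tier 4 limit, Table GPHL.4.9 itself concludes Not Present even when Tier 2 is Detected. It would be inconsistent to call the same sample Inconclusive because Tier 2 was Not Detected. So two combinations should change outright, and the third only if the drug level is also at or above the Tier 4 limit.

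**Step 4: which samples are exposed.** Only ADA Present samples go to Tier 2b and 2c. The note under Table GPHL.4.9, which makes neutralising results Inconclusive for an ADA Inconclusive sample, therefore does not reach them. A Detected result in the general ADA assay does not show that Tier 2b or 2c could see antibody at that drug level, since the SAP treats them as separate assays.

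**The case against.** The case for leaving the text alone has several parts.

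- **The list of Inconclusive results in 4.6.5.5.1 names only the two Tier 4 assays, and the in silico step is described as run only when cross-reactive antibody is detected.** True, but that list concerns the neutralising result. Table GPHL.4.9 classifies Not Detected rows anyway, and 4.6.5.5.4 says the classification will be summarised. The testing flowchart is not visible in the copy available and might add something. If Tier 2b and 2c are free of drug interference, the SAP should say so.
- **Exposure may be small or nil.** This stands. It is not known whether clinical concentrations ever reach a Tier 2b/2c limit, and the participant cases above are constructed, with no estimate of frequency.
- **The deciding sample in the participant rule is a Detected one, hence informative, and no sample is relabelled.** Both statements are right. The remaining samples are still uninterpretable, exactly as in the comparison case that the SAP calls Inconclusive.
- **There are mitigations.** The Visit 801 sample is taken at washout (Protocol 8.9), analyses also cover the whole postbaseline period, and 4.6.5.5.4 lists every participant with ADA Present at any time, sample by sample. Each participant-rule case has such a sample, so it will be visible in the listing. That limits the harm but does not correct the tables.
- **The adverse-event summary is descriptive, with no stated test.** This also stands.

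**Conclusion.** The point holds in a limited form. On its literal text the participant rule makes some people TE ADA-negative who would be Inconclusive with a cleaner sample. Table GPHL.4.9 is inconsistent with the drug-tolerance rule only for ADA Present samples with a measured concentration at or above the Tier 2b/2c tolerance. This rests on reading the extension of the Table GPHL.4.8 terminology as covering its Inconclusive category. The size in participants cannot be computed: the documents give no tolerance limits, concentrations or antibody rates.

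A reader might infer more than the documents support:
- **That the TE ADA+ rate is understated.** It is not. Both changes move labels between negative and Inconclusive; TE ADA+ counts and the evaluable denominator stay the same.
- **That missing concentrations are mishandled in Table GPHL.4.9.** That part follows the convention stated openly in Table GPHL.4.8.
- **That every Tier 2b/2c Not Detected result above tolerance is false.** Above tolerance it is unverified, and a valid Tier 4 negative can still support Not Present.
- **That a percentage of results is affected.** Any such figure would have no source here.

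No efficacy result or multiplicity-controlled test is touched. This is a correction to descriptive safety classifications.

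**What to change.** 1. In SAP 4.6.5.5.3, keep the 20% limit for TE ADA Inconclusive, but replace the condition on the remaining samples with the condition that no postbaseline sample meets the TE ADA+ criteria. Evaluable participants who are not TE ADA+ then divide cleanly at 20%.
2. In Table GPHL.4.9, for Tier 2b (2c) Not Detected, keep Not Present when the concentration is below the Tier 2b (2c) tolerance, when it is missing, when the participant is on placebo, or when Tier 4a (4b) is Not Detected with the concentration below its own tolerance. Otherwise classify as Inconclusive. The missing and placebo cases must be named, or those samples would have no classification.
3. As an alternative to item 2, state why Tier 2b and 2c are not subject to drug interference, and reconcile Tables GPHL.4.8 and GPHL.4.9 accordingly.

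The cost is SAP wording and a few lines of derivation code, with no new samples. The downside is that some Not Present or TE ADA-negative results become Inconclusive, which is a less reassuring display.

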4.6.5.5.2. Definitions of Immunogenicity Assessment Periods

Immunogenicity Baseline Observations: Baseline period for immunogenicity assessment for each participant includes all observations up to baseline visit. In instances where multiple baseline observations are collected, to determine participant ADA status the last nonmissing immunogenicity assessment up to first administration of study intervention is used to determine treatment-emergent status (see below).

Immunogenicity Postbaseline Period Observations: Postbaseline period observations for each participant include all observations after the first administration of study drug. There are 2 different periods listed below:

- The planned treatment period is defined as from the first dose of treatment to end of the treatment period.
- The entire postbaseline period is defined as from the first dose of treatment to the end of safety follow-up visit or date of study withdrawal.

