8.3.2.8. Injection Site Reactions

Symptoms of a local injection site reaction may include erythema, induration, pain, pruritus, and edema. If an injection site event is reported, the AE will be recorded, and additional data will be provided to the sponsor in the Injection Site Reaction eCRF.

At the time of AE occurrence, samples will be collected for measurement of tirzepatide antidrug antibody (ADA) and tirzepatide concentration.

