8.9. Immunogenicity Assessments

Where local regulations and ERBs allow, blood samples for immunogenicity testing will be collected to determine antibody production against tirzepatide as specified in the SoA (Section 1.3).

For immunogenicity testing, venous blood samples will be collected from each participant according to the SoA (Section 1.3) to determine antibody production against tirzepatide. To interpret the results of immunogenicity, a venous blood sample will be collected at the same time points to determine the plasma concentrations of tirzepatide. All samples for immunogenicity should be taken predose when applicable and possible.

In the event of systemic drug hypersensitivity reactions (immediate or nonimmediate), additional unscheduled samples should be collected as detailed in Section 8.3.2.7 (Hypersensitivity Reactions). Instructions for the collection and handling of blood samples will be provided by the sponsor. The actual date and time (24-hour clock time) of each sampling will be recorded. Sample collected at Visit 801 will assess immunogenicity at washout of tirzepatide (5 half-lives post end of treatment).

Immunogenicity will be assessed by a validated assay designed to detect ADAs in the presence of tirzepatide at a laboratory approved by the sponsor. Antibodies may be further characterized for their ability to neutralize the activity of tirzepatide on GIP and GLP-1Rs. Positive tirzepatide ADA samples will be tested for cross-reactivity with native GIP and GLP-1, and, if positive, may then be tested for neutralizing antibodies against native GIP and/or GLP-1. In vivo laboratory indicators for effect on weight loss and PK will be utilized to detect potential neutralizing effect of ADAs against tirzepatide.

Treatment-emergent ADAs are defined in Section 9.4.6.

Samples will be retained for a maximum of 15 years after the last participant visit, or for a shorter period if local regulations and ERBs allow, at a facility selected by the sponsor. The duration allows the sponsor to respond to future regulatory requests related to tirzepatide. Any samples remaining after 15 years will be destroyed.

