10.3. Appendix 3: Laboratory Assessments for Hypersensitivity Events

- Laboratory assessments should be performed if the participant experiences generalized urticaria or if anaphylaxis is suspected.
- Collect sample after the participant has been stabilized, and within 1 to 2 hours of the event; however, samples may be obtained as late as 12 hours after the event as analytes can remain altered for an extended period of time. Record the time at which the sample was collected.
- Obtain a follow-up sample at the next regularly scheduled visit or after 4 weeks, whichever is later.

The table below summarizes the laboratory parameters that will be evaluated. These laboratory tests are bundled in the hypersensitivity laboratory testing kit.

Clinical Lab Tests for Hypersensitivity Events

Hypersensitivity Tests	Notes
Tirzepatide ADAs (immunogenicity/ADA)	Selected test may be obtained in the event of anaphylaxis or systemic allergic/hypersensitivity reactions.
Tirzepatide concentrations (PK)	Assayed by Lilly-designated laboratory. Results will not be provided to the investigative sites.
Tryptase	
Assayed by Lilly-designated laboratory. Results will not be provided to the investigative sites.
 
Note: If a tryptase sample is obtained more than 2 hours after the event (that is, within 2 to 12 hours), or is not obtained because more than 12 hours have lapsed since the event, obtain urine sample for N-methylhistamine testing. Note that for tryptase serum samples obtained within 2 to 12 hours of the event, urine N-methylhistamine testing is performed in addition to tryptase testing. Collect the first void urine sample following the event. Obtain a follow-up urine sample for N-methylhistamine testing at the next regularly scheduled visit or after 4 weeks, whichever is later.

N-methylhistamine	Assayed by Lilly-designated laboratory. Results will not be provided to the investigative sites.
Drug-specific IgE	
Will be performed if a validated assay is available.
 
Assayed by Lilly-designated laboratory. Results will not be provided to the investigative sites.

Basophil activation test	
Will be performed if a validated assay is available.
 
Assayed by Lilly-designated laboratory. Results will not be provided to the investigative sites.
 
Note: The basophil activation test is an in vitro cell based assay that only requires a serum sample. It is a surrogate assay for drug specific IgE, but is not specific for IgE.

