4.6.5.5.4. Analyses to be Performed

The count and proportion of participants who are TE ADA+ will be tabulated by treatment group, where proportions are relative to the number of TE ADA-evaluable participants, as defined above. The tabulation will include the count and proportion of participants with ADA Present at baseline and the count and proportion of TE ADA+ participants exhibiting each type of cross-reactive antibodies and NAb. This analysis will be performed for

- the planned treatment period, and
- the entire postbaseline period including safety follow-up.

The *in silico* classification for cross-reactive NAb will be summarized.

A summary will be provided of the count and percentage of tirzepatide-treated participants experiencing specific TEAE (see [Table GPHL.4.10](#)) by TE ADA status (TE ADA+, TE ADA-, TE ADA Inconclusive) during the planned treatment period.

Table GPHL.4.10. Adverse Events for Analysis with Immunogenicity Results

TEAE category	Criteria
Hypersensitivity reactions	Anaphylaxis SMQ (narrow or algorithm)
	Hypersensitivity SMQ (narrow)
	Angioedema SMQ (narrow)
	Severe Cutaneous Adverse Reaction SMQ (narrow)
	Vasculitis SMQ (narrow)
Injection site reactions	Injection site reaction HLT
	Infusion site reaction HLT
	Administration site reaction HLT

Abbreviations: HLT = High Level Term; MedDRA = Medical Dictionary for Regulatory Activity; SMQ = Standardised MedDRA Query; TEAE = treatment-emergent adverse event.

A listing will be provided for all participants who had ADA Present at any time (including baseline) or had any specific TEAE (see [Table GPHL.4.10](#)). This listing includes a time course of ADA (clinical interpretation result plus flags for samples meeting TE ADA+ criteria and for samples with cross-reactive antibodies and NAb present) along with the TEAE.

Cases of TE ADA that are associated with TEAEs of either severe/serious hypersensitivity or injection site reactions will be classified as AESIs.

Additional immunogenicity analyses as determined later may be presented. The relationship between antibody titers, the PK parameters, and PD response to tirzepatide may also be assessed.

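### ADA samples drawn because of a reaction count toward TE ADA status, and reactions are then summarised by that status, so the table can show an association that comes from sampling alone

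*SAP*

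**What the plan says.** **Which samples count.** SAP 4.6.5.5.2 states: "Postbaseline period observations for each participant include all observations after the first administration of study drug". It defines two assessment periods. The one used for the reaction summary is a time window, not a list of visits: "The planned treatment period is defined as from the first dose of treatment to end of the treatment period".

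**How status is set.** Under SAP 4.6.5.5.3, a participant without ADA at baseline is TE ADA+ with "at least 1 postbaseline status of ADA Present with titer" at or above twice the minimum required dilution. A participant with ADA at baseline needs one post-baseline titre at least four times the baseline titre. A participant is TE ADA Inconclusive if at least 20% of the "postbaseline samples are ADA Inconclusive and all remaining postbaseline samples are ADA Not Present".

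**What triggers extra samples.** For injection site reactions, Protocol 8.3.2.8 states: "At the time of AE occurrence, samples will be collected for measurement of tirzepatide antidrug antibody (ADA) and tirzepatide concentration". For hypersensitivity, Protocol 8.9 states: "In the event of systemic drug hypersensitivity reactions (immediate or nonimmediate), additional unscheduled samples should be collected". Protocol 8.9 refers for detail to 8.3.2.7, which ties the samples to generalized urticaria or anaphylaxis. Protocol 10.3 lists ADA in the test kit ("Selected test may be obtained in the event of anaphylaxis or systemic allergic/hypersensitivity reactions") and asks for a later follow-up sample.

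**How status is used.** SAP 4.6.5.5.4 states: "A summary will be provided of the count and percentage of tirzepatide-treated participants experiencing specific TEAE", split by TE ADA+, TE ADA- and TE ADA Inconclusive. The events, in Table GPHL.4.10, are hypersensitivity and injection site reactions. The same section plans a participant listing with the ADA time course. It also classes TE ADA cases associated with severe or serious reactions as adverse events of special interest (AESIs).

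**The concern.** TE ADA status follows an ever-positive rule, so the chance of being TE ADA+ rises with the number of samples. If a reaction adds a sample, participants with reactions have more chances to be classed as positive. The table can then show more reactions among TE ADA+ participants even when antibodies and reactions are unrelated.

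This is the summary of reactions by antibody status that the SAP commits to. An excess produced by sampling would read as immune-mediated reactions, which is a safety conclusion.

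The point looks like an omission, not a choice. For laboratory tests, vital signs and ECGs, Table GPHL.4.1 says whether unscheduled measurements count, and it sends immunogenicity to SAP 4.6.5.5. That section settles which sample to use when there are several at baseline. It says nothing about unscheduled samples after baseline.

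**Working it through.** The documents give no figure on this point, so there is none to reproduce. The check asks what the table would show if ADA and reactions were independent.

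**Inputs from the documents**
- Scheduled post-baseline ADA samples in the treatment period: k = 5 for a completer (Weeks 4, 12, 24, 48 and 72). These are read from the immunogenicity row of the Schedule of Activities (Protocol 1.3), whose columns are shifted in the text available.
- Extra samples per participant with a reaction: m, from Protocol 8.3.2.8, 8.9 and 10.3.

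**Inputs assumed (not in the documents)**
- Reaction risk r = 5%.
- Fraction with persistent ADA, always caught at a scheduled visit: π from 0 to 0.5.
- Per-sample chance of a qualifying transient titre in the others: p from 0 to 0.20, independent between samples.

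**Formulas**
- TE ADA+ without a reaction: a = π + (1−π)[1−(1−p)^k]
- TE ADA+ with a reaction: b = π + (1−π)[1−(1−p)^(k+m)]
- Apparent risk ratio = [r·b/(r·b+(1−r)·a)] ÷ [r(1−b)/(r(1−b)+(1−r)(1−a))]

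**Worked case** (π = 0, p = 0.10, k = 5, m = 1)
- a = 1 − 0.9^5 = 0.410 and b = 1 − 0.9^6 = 0.469.
- Reaction risk is 0.0568 in TE ADA+ and 0.0452 in TE ADA-, a ratio of 1.26. The true ratio is 1.

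**Results with five scheduled samples**

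| Scenario | TE ADA+ without reaction | m = 1 | m = 2 | m = 4 |
|---|---|---|---|---|
| Persistent only (π = 0.5, p = 0) | 50.0% | 1.00 | 1.00 | 1.00 |
| π = 0.4, p = 0.02 | 45.8% | 1.04 | 1.09 | 1.17 |
| π = 0.4, p = 0.10 | 64.6% | 1.16 | 1.34 | 1.76 |
| Transient only, p = 0.02 | 9.6% | 1.20 | 1.40 | 1.80 |
| Transient only, p = 0.10 | 41.0% | 1.26 | 1.54 | 2.19 |
| Transient only, p = 0.20 | 67.2% | 1.35 | 1.79 | 3.01 |

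Fixing the transient-only TE ADA+ proportion P on five samples, b = 1 − (1−P)^((5+m)/5). For m = 1 and 2 this gives 1.23 and 1.48 at P = 30%, and 1.28 and 1.60 at P = 50%.

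With only two scheduled samples (transient only, p = 0.10), the ratios are 1.54, 2.13 and 3.44 for m = 1, 2 and 4.

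**Scheduled samples only.** The number of samples entering status is then k in both groups, so a = b and the ratio is 1.00. A simulation of 2,000,000 participants (π = 0.4, p = 0.10, m = 2) gave 1.35 with all samples and 1.01 with scheduled samples only.

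**Fewer samples after a reaction.** If a participant with a reaction ends with four samples in total (m = −1, P = 30%), b = 0.248 and the ratio is 0.78. With three samples it is 0.57.

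**Inconclusive rule.** One inconclusive sample of five is 20% and meets the threshold. One of six is 16.7% and does not. A single extra ADA Not Present sample therefore moves the participant from TE ADA Inconclusive to TE ADA-.

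**The case against.** Several counter-arguments have force.

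- **Direction for systemic hypersensitivity.** A reader might infer that every participant with a reaction is pushed toward TE ADA+. The documents do not support that. Protocol 7.1 provides for permanent discontinuation of study drug after a drug-related systemic reaction. Such participants are asked to keep attending, but those who decline are asked back only for Visit 99, whose procedures in Protocol 4.1.1.2.2 include no ADA sample. They can end with fewer samples, and the ratio can fall below 1. This stands, though it bears less on injection site reactions.
- **Not every listed event triggers a sample.** The hypersensitivity rows of Table GPHL.4.10 cover narrow terms of five SMQs, while Protocol 8.3.2.7 and 10.3 concern generalized urticaria or anaphylaxis. The follow-up sample is due at the next scheduled visit or after 4 weeks, whichever is later, so it may coincide with a routine ADA visit. If only half of participants with reactions gain one extra sample, the ratio falls to 1.11 (P = 30%) or 1.13 (P = 50%). This stands.
- **Drug interference.** Event samples may not be taken before dosing. Higher drug levels could make some inconclusive and lower detection, so treating them as equally likely to be positive may overstate the effect.
- **Limited use.** The summary gives counts and percentages with no planned test, and the listing shows which samples met the TE ADA+ criteria. That allows case-by-case checking but does not correct the percentages in the table. Nor is this the only assessment possible: Protocol 9.4.6 and SAP 4.6.5.5.4 leave room for others, though none is committed to.
- **Cost of dropping event samples.** Basing status on scheduled samples alone could hide antibodies truly present at the reaction. It could also make the same person a TE ADA-associated AESI and TE ADA- in the table. This is a good reason to show both versions and not to replace one with the other.

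**Conclusion.** The concern holds as a design weakness in one descriptive safety summary. As written, the SAP counts reaction-triggered samples toward an ever-positive status and then summarises reactions by that status. No section limits status to scheduled samples, requires ADA to precede the reaction, or plans a scheduled-only version. The table can therefore show an association that comes from sampling alone.

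The case is clearest for injection site reactions, where each reported event calls for a sample. For systemic hypersensitivity the direction is uncertain.

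The size is not derivable from the documents. With five scheduled and one or two extra samples, the apparent null ratio runs from about 1.0 (persistent ADA) to about 1.5 to 1.6 (fully transient ADA with 30% to 50% positive). It reaches 1.79 if 67% are positive, and is higher with recurrent reactions or few scheduled samples. All of this rests on the assumed 5% reaction risk, positivity and persistence.

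A reader might take the upper figures as the expected bias, or conclude that an excess in the TE ADA+ row must be spurious. Neither follows: persistent ADA would remove the effect, and a true association remains possible.

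**What to change.** In SAP 4.6.5.5.4, produce the summary of Table GPHL.4.10 events by TE ADA status in two versions, side by side:

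1. status from all samples, as now;
2. status from scheduled visit samples only, including the 20% Inconclusive count.

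State that an ADA-reaction association is not to be concluded from the all-samples version alone. Keep all samples for overall TE ADA incidence, AESI classification and the time-course listing, so that no case is lost.

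List the visits that count as scheduled, and say how the early discontinuation visit is treated. Table GPHL.4.1 counts that visit as scheduled for change analyses, but a reaction that leads to stopping treatment also brings about the visit and any ADA sample taken there.

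The cost is a visit filter in the program and one extra table; no new data are needed. The downside is that a participant positive only on an event sample appears as TE ADA- or Inconclusive in the scheduled-only version, which the adjacent table and the listing make visible.
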